5.1. STUDY RISK / BENEFIT ANALYSIS

Benefits: The only tests of clinical significance to the child are the skin prick tests, which might for example inform a decision about the purchase of a pet. The family will be informed about these results. The other tests won't be of clinical significance. The ultimate benefit will be in the future if we can show with a large intervention trial that measuring one or more of these biomarkers helps predict future wheezing exacerbations as well as guide treatment more efficiently, thus children stop receiving unnecessary medications. The benefit generated by this trial is to show that these markers can be measured in practice, and they are acceptable to the families.

Risk analysis: Child participants' routine clinical management is not changed in this observational study. Clinicians have no access to study data. Risks relate to study procedures: all procedures [blood sampling through finger prick test, skin prick tests and FeNO collection (offline method)] will be performed by trained research personnel.

Skin prick tests are safe and used clinically for many years, but adrenaline and antihistamines will be available while the study procedures are being performed, in the highly unlikely event of an allergic reaction (Figure 1). All research staff will be trained in management of acute reactions / anaphylaxis. The finger prick test is the same as used by diabetic patients to monitor blood glucose. Collecting breath into a bag is devoid of risk.

[figure not shown]

Figure 1. Anaphylaxis case reports after skin prick test. (A) Clinical study in Cambridge, UK involving 31,000 participants (17), (B) Retrospective analysis from 4 allergy centres in Italy (Verona, Genoa and Naples) involving 55,105 participants (18).

6. STUDY DESIGN

This is a pragmatic, observational study involving preschool children with wheeze aged one to five years old. All treatment and routine monitoring decisions will be at the discretion of their treating general practitioner (GP) or paediatrician (as per usual clinical practice), blinded to the study measurements. After clinical consultation and following submission of the electronic informed consent through the Qualtrics® platform (offered by Imperial College London), the parent/carer will be asked to give the contact details of the child's GP or paediatrician, who will be informed about child's participation in this study through a letter sent to his/her email along with the patient information sheet. The parent carer will be then shown a standard video questionnaire and will be asked to identify what respiratory sounds their children have been making. The child will be booked for the three biomarker tests [atopic sensitisation, blood eosinophil count and FeNO (off-line method)]. The tests will be carried out once and at a time of clinical stability. In this visit, a sample of the child's exhaled tidal breath will be collected in a suitable bag in duplicate for offline measurement of FeNO later on with chemiluminescence. Skin prick tests will be performed to: (a) house dust mite, (b) grass pollen, (c) tree pollen, (d) cat hair(e) dog hair, as well as normal saline and histamine and these will be applied on either the child's back, leg or arm. If the child has been prescribed antihistamines, we will ask for these to be withheld for 72 hours prior to skin prick testing. FeNO values (offline method) ≥ 10 ppb will indicate Type 2 inflammation and wheal diameter, measured with a specialised skin prick test ruler, ≥ 3 mm will indicate sensitisation to the applied aeroallergen. In addition, skin prick tests will allow the assessment of which aeroallergen is the most useful predictor of outcomes in preschool children. Finally, the peripheral blood eosinophil count will be measured from a finger prick blood sample, using the Haemocue machine, allowing a result in approximately 2 minutes. Values ≥ 300 cells/ μ l indicate Type 2 inflammation. All tests will normally take no more than one hour.

The recruitment period will approximately last 9 months, and all preschool wheezers can join the study at any point (Appendix 1: Recruitment Plan). Parents/Carers of preschool children presenting to primary care or to the Emergency Department (ED) or to secondary care (e.g., outpatients) as well as those identified from primary care records and who have been diagnosed by a GP or paediatrician with wheezing, will be approached by collaborating doctors and nurses who will ask their parents if they are willing to have their child participate in the study (Appendix 1: Recruitment Plan). A patient information sheet will be given, containing all the information regarding the project and the contact details of the research team, for further questions. They will be asked for their willingness to give the study team permission to contact them and discuss recruitment, and if so, they will submit their contact details in an electronic form made with Qualtrics® questionnaire platform (offered by Imperial College London), which allows gathering data according to the GCP guidelines and as used for years in the Breathing Together study (19). This form will be available online in the Asthma UK Centre for Applied Research's (AUKCAR) website. The initial introduction

will be made either by the clinical team (above) with the study team contacting them at a later date to give more information or by [name] if he is there in person.

Additionally, the Emergency Department of Oxford Universities Hospital (OUH) Trust will identify patients who have previously presented and diagnosed with wheezing in the Emergency Department. A regular search of the OUH databases will be performed by the clinical care team to identify patients who meet the eligibility criteria and have attended the Emergency Department. Parents/carers of eligible participants will be informed about the study by phone by a member of their clinical care team and asked whether they agree to be contacted by the study team to give them more information and send them the participant information sheet. Their contact details will be then submitted in the TAILOR study contact details form.

If the child has been prescribed OCS, testing will be delayed by 2 weeks for biomarker testing as soon as the electronic informed consent is submitted. Finally, parents will be informed through the patient information sheet as well as, in person, that a second optional testing will take place 3 months after the first one, in their second study visit. This will allow assessing the reproducibility of the obtained biomarker results, thus additionally assess their stability.

Patient recruitment at a site will only commence once the study team has ensured the following:

- HRA approval
- Completed Local Site Delegation of Duties and Signature Log
- Confirmation of Capacity and Capability

All recruitment procedures will be in accord with the GCP, and parents/carers will be given detailed information regarding the study as well as all the time they need to understand it. Parents/guardians have at least 24 hours to consider participation. Recruitment will only commence after parents/carers have fully understood the project and given informed consent online through the Qualtrics® platform (offered by Imperial College London).

Child participants entering the study upon their parents' wish, will be fully screened by the Principal Investigator (PI) or someone else from the research team who is suitably qualified and delegated to do so, with the latter taking informed consent as well. After the electronic informed consent sheet is submitted, parents will be asked to provide the contact details of their child's GP or paediatrician, to inform him/her about the child's participation in this study through a letter sent by email along with this patient information sheet. In addition, we will ask them to provide some of the child's personal data (Appendix 1: Recruitment Plan, Table 3: The personal data that will be obtained

by each individual participant). Children's full name, date of birth, gender, ethnicity as well as, their parent's full name, telephone number and email address will be added in the child's patient card. All other data obtained from the study will be added in the Case Report Form (CRF).

Follow-up: We will arrange for a short monthly electronic questionnaire to be sent by email to the parents/carers, in order to record on a monthly basis, the days their child was out of childcare, days the carer missed from work, unscheduled health care visits and use of rescue therapy or oral corticosteroids (including dosage) (Appendix 4: Monthly Questionnaire). In addition, we will record the children's TRACK™ score (Test for Respiratory and Asthma Control in Kids) (Appendix 3: TRACK™ score questionnaire) every 3 months, to assess wheeze control. The questionnaires will be made and sent through the Qualtrics® questionnaire platform (offered by Imperial College London). There will be review visits every 3 months, to evaluate their progression in person, but if not feasible, video calls will be arranged through Microsoft Teams. Correct use of spacers will be ensured after guiding parents on how to use them and will be done by their GP or paediatrician as well as from [name] who is a registered pharmacist in the UK.

In the event that a child has had their ICS treatment discontinued, we will record whether this was because the treatment was ineffective (treatment failure) or if the child was so well that the family or GP did not wish to continue (treatment success or spontaneous improvement). If an additional medication is prescribed, or the child is referred to secondary care, this will be considered as treatment failure. When the study ends, participants' parents/carers will be invited to a face-to-face focus group interview, or a one-to-one interviews, or remotely through Microsoft Teams, depending on their availability at the end of the study period. The focus group and one to one interviews will utilise a semi structured questionnaire, to provide qualitative feedback on the acceptability of the 3 biomarker tests. In addition, a separate focus group for doctors and nurses will be conducted to assess the feasibility of the 3 biomarker tests being used in clinical practice. They will be given all the information regarding the study as well as the study's patient information sheet. Those agreeing to take part, will sign a consent form. They will be attending either a face-to-face focus group interview, or a one-to-one interview, or remotely through Microsoft Teams, depending on their availability. A semi structured questionnaire will be utilised. Where possible a second independent researcher will sit in the focus groups discussion and interviews to ensure there is no bias. The conversations from the focus group and one to one interviews will be transcribed and coded into themes. We will utilise an external company for transcribing the conversations called 1st Class. <https://www.1stclass.uk.com/>

The focus group and one to one interviews will be audio recorded, transcribed and put into themes to conduct an inductive thematic analysis. 25% of the transcripts will be

double coded by an independent researcher, experienced in qualitative research to ensure that the correct themes have been used and to ensure that there is no bias. The focus group and one to one interviews will be used to assess the acceptability and feasibility of measuring biomarkers in primary care and using them to help determine management of preschool wheeze.

In addition, we will ask them to fill in a very short electronic questionnaire after the study is finished, to check their perspective and acceptability on these biomarkers being used to guide children's therapy in the future (Appendix 5: Exit Questionnaire).

The whole duration of this study is expected to be 20-21 months, with 1-year follow-up for each patient included.

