The Lancet Asthma Commission has highlighted that 'asthma' is an umbrella term for a clinical syndrome comprising wheeze, chest tightness, breathlessness and sometimes increased cough (2). The focus has moved to defining so-called 'treatable traits', such as whether there is eosinophil airway inflammation, usually driven by the signature Type 2 cytokines Interleukin (IL) -4, -5, and -13, which are responsive to inhaled corticosteroids (ICS) (6,7). Nowhere is this concept of treatable traits more important than in preschool wheeze, wherein only a few children who wheeze have any evidence of allergic sensitisation or Type 2 inflammation. At age one year, even children with such severe symptoms as to merit bronchoscopy in a tertiary referral children's hospital had no evidence of any inflammation or airway remodelling (8). By 30 months of age, in another cross-sectional study, some but by no means all had evidence of eosinophil airway inflammation, reticular basement membrane thickening and airway smooth muscle hypertrophy and hyperplasia (9). Clinical experience reflects this diversity, and although atopic preschool wheezers are more likely to respond to ICS, as we have shown, many atopic wheezers do not have an eosinophil airway phenotype (10), and are thus unlikely to be ICS responsive. We have recently confirmed that there is a good correlation between bronchoalveolar lavage and peripheral blood eosinophil concentrations (11).

Another biomarker for eosinophil airway inflammation is exhaled nitric oxide (FeNO). In older children and adults, titrating ICS dose using FeNO has been shown to reduce asthma attacks and improve outcomes (12). The use of FeNO to guide management not been studied in pre-school children. Young children usually cannot perform the standard slow exhalation, but we have experience in measuring FeNO off-line by collecting tidally exhaled air, which is the technique we propose to use.

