5. STUDY'S AIM AND OBJECTIVES

AIM: To obtain pilot data to test the hypothesis that aeroallergen sensitisation (confirmed by a wheal formation with a diameter ≥ 3 mm after a skin prick test is performed), FeNO (offline method) ≥ 10 ppb and a peripheral blood eosinophil count $\geq 300/\mu\text{l}$, alone or in combination, can predict future wheezing exacerbations in preschool children as well as response to treatment with inhaled corticosteroids, as a preliminary to a large, randomised controlled trial. Also, that these tests are acceptable to families.

OBJECTIVES:

- To recruit 100 preschool children with a history of wheeze, aged one to five years old, and determine atopic status, peripheral blood eosinophil count (point of care test) and FeNO (offline method).
- To evaluate the feasibility and acceptability of these tests
- To categorize the children according to the biomarkers tested and assess whether any or all, alone or in combination, predict future wheezing exacerbations as well as determine the clinical outcome over one year
- To obtain parents' and doctors' insights into whether the biomarkers mentioned above could be used in a future intervention study.

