6.1. STUDY OUTCOME MEASURES

Primary outcome:

Acute attacks of wheeze defined as requiring an unscheduled health care visit

Secondary outcomes:

- Carer days off work
- Days the child unable to attend childcare facility
- Use of oral corticosteroids
- Use of inhaled β -2 agonist (rescue therapy)
- Assessment if children's respiratory or wheezing condition is under control by using the TRACK™ score questionnaire (Test for Respiratory and Asthma Control in Kids) (Appendix 3).

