11. STATISTICS AND DATA ANALYSIS

The statistical analysis of the project will be done by [name] in collaboration with [name] (University of Edinburgh) and the Asthma UK Centre for Applied Research (AUKCAR), the funder of the study. Statistical analyses will use the GraphPad PRISM software package. A normality test will be performed to assess normal (Gaussian) distribution (e.g., the Shapiro-Wilk test. If there is normal distribution, then parametric tests will be used, otherwise non-parametric tests. Level of significance is set as a p value <0.05. The tests that are currently planned to be used are:

- **Chi-Squared test (x²-test)**

This test allows assessing if a variable is similar between two or more groups or to test if two or more variables are related/dependent

- **Fisher's Exact test**

This test is used when chi-squared values are <5, usually with a small sample size.

- **Student t-test or Mann-Whitney test**

These tests are used for comparison between two study groups. The first is for normally distributed quantitative variables and the second for non-normally distributed quantitative variables.

Data and all appropriate documentation will be stored for a minimum of 10 years after the completion of the study, including the follow-up period.

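### With 100 children and no planned comparison between allergens, the study cannot reliably rank five aeroallergens as predictors, though Sections 6 and 7.1 say it can assess which is most useful.

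*Combined protocol and SAP*

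**What the plan says.** Section 6 (Study Design) says "skin prick tests will allow the assessment of which aeroallergen is the most useful predictor of outcomes in preschool children", and Section 7.1 repeats the sentence. Neither place qualifies it.

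- **Panel.** "Skin prick tests will be performed to: (a) house dust mite, (b) grass pollen, (c) tree pollen, (d) cat hair(e) dog hair", so five allergens. A wheal "≥ 3 mm will indicate sensitisation to the applied aeroallergen", so each allergen gives its own yes/no result and one child can be positive to several.
- **Size.** Section 5: "To recruit 100 preschool children with a history of wheeze, aged one to five years old". No sample-size reasoning is given.
- **Expected positives.** No figure is given. Section 4.1 remarks that "only a few children who wheeze have any evidence of allergic sensitisation or Type 2 inflammation".
- **Outcome.** Section 6.1: "Acute attacks of wheeze defined as requiring an unscheduled health care visit", "with 1-year follow-up for each patient included" (Section 6). No expected attack rate is given.
- **Analysis.** Section 11 lists chi-squared, Fisher's exact, Student t and Mann-Whitney tests. "Level of significance is set as a p value <0.05". It describes no comparison between allergens, no handling of children positive to more than one, and no multiplicity control.
- **Exploratory label.** Section 4.1 applies this to the analysis of summed wheals. It is not attached to the comparison of allergens.

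**The concern.** The sentence gives the study an ability that neither its size nor its analysis section supports. Saying which of five allergens is the most useful predictor means comparing five associations with one another, and each rests on the subset of 100 children positive to that allergen. The subsets can share children, so even a chi-squared test across several groups would not apply directly: a child positive to cat and dog would belong to two groups at once.

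Without an exploratory label, the allergen with the largest ratio or the smallest p-value could be reported as the most useful one when sampling error had put it there. In a study meant to supply pilot data for a larger trial, a reader might carry that result forward with more confidence than it deserves.

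**Working it through.** The plan states no power, effect size, prevalence or attack rate, so there is no figure of its own to reproduce.

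**Inputs from the protocol:** 100 children; 5 allergens; positive at 3 mm or more; one year of follow-up; significance at 0.05 (taken as two-sided).

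**Assumed inputs:** prevalence per allergen, attack frequency, effect sizes and overlap between allergens. Ranges are shown.

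**1. Children per allergen.** Expected positives are 100 × prevalence: 5, 10, 15, 20 and 30 at 5, 10, 15, 20 and 30%. The 95% binomial ranges are 1-10, 5-16, 8-22, 12-28 and 21-39. If 5 of 10 positive children have an attack, the exact 95% CI for that risk is 18.7-81.3%.

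**2. One allergen against children not sensitised to it.** Let n1 children be positive and n0 = 100 − n1 not, with risks p1 and p0 of at least one attack and pooled risk p. Then

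power ≈ Φ[(|p1 − p0| − z·s0)/s1], where s0 = √[p(1−p)(1/n1 + 1/n0)] and s1 = √[p1(1−p1)/n1 + p0(1−p0)/n0].

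Example with n1 = 15, p1 = 0.60, p0 = 0.40:
- p = (15×0.60 + 85×0.40)/100 = 0.43
- s0 = √[0.43×0.57×(1/15 + 1/85)] = 0.139
- s1 = √[0.24/15 + 0.24/85] = 0.137
- power = Φ[(0.20 − 1.96×0.139)/0.137] ≈ 30%
- CI half-width for the risk difference = 1.96×0.137 ≈ 27 points

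Across 5-30% prevalence and 30-50% risk in the unsensitised:

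| True difference | Power, α = 0.05 | Power, α = 0.05/5 = 0.01 |
|---|---|---|
| 20 points | 12-48% | 3-26% |
| 30 points | 21-83% | 6-60% |

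Power reaches 80% only for a 30-point difference at 30% prevalence with unadjusted α. Five unadjusted tests carry a familywise error of up to 1 − 0.95⁵ = 22.6% (less if correlated).

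**3. One allergen against another.** Only children positive to one of the pair and not the other separate the two. With 10-30% prevalence and 40-60% overlap, that leaves from 100×0.10×0.40 = 4 to 100×0.30×0.60 = 18 children on each side. Power for 60% against 40% is 8-22%. For 80% power, 97 children are needed on each side, so about 97/0.18 ≈ 540 to 97/0.04 ≈ 2400 children in total.

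**4. How often the best allergen comes first.** Simulation of 100 children and five allergens with equal prevalence of 6-20% and latent correlation 0.5. Attacks are negative binomial with variance = mean + mean²/k. Allergens are ranked by observed rate ratio. The lower end of each range is at 6% prevalence, the upper end at 20%.

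| Best allergen doubles the rate; other four | Mean 1 attack, k = 1 | Mean 2 attacks, k = 2 |
|---|---|---|
| no effect | about 51-72% | about 63-88% |
| each raises the rate by 30% | about 38-54% | about 44-67% |

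Chance is 1/5 = 20%. Tie handling and simulation error move these by two or three points. If the best allergen multiplies the rate by 1.5 and the others do nothing, it comes first in 37-50% (mean 1, k = 1). At 20% per allergen, about 49% of children would be sensitised to something, which is high beside the remark in Section 4.1.

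A separate simulation on a yes/no outcome agrees. With an odds ratio of 3 for the best allergen and 10-30% prevalence, it ranks first in 54-80% if the others have no effect and in 43-55% if each has an odds ratio of 1.5.

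**The case against.** The strongest reply is context. Ranking allergens is not in the aim, the objectives or the outcomes. It is one supplementary sentence in a study titled a feasibility study, and Section 5.1 describes its benefit as showing that the markers can be measured and are acceptable to families. The wording speaks of allowing an assessment, which is softer than promising to identify a winner. Section 11 calls its tests those currently planned, and a chi-squared or Fisher test can describe each allergen's own association with attacks. Wheal diameter is measured too and could add information that yes/no sensitisation loses.

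Much of this stands, and it keeps the point to one of wording and labelling. It does not remove it: the sentence still speaks of which allergen is the most useful, and describing five associations separately does not rank them.

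A reader might also infer stronger things that the documents do not support:
- **That a ranking would be close to chance.** The simulated figures, 37-88%, are all well above 20%.
- **That only a handful of children will be positive to each allergen.** The remark in Section 4.1 gives no number, concerns wheezing children in general, and covers sensitisation or Type 2 inflammation. This study also recruits from emergency departments and secondary care.
- **That the ranking will choose the extracts for the later trial.** Nothing in the protocol says so.

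**Conclusion.** The point holds in a limited form: the study cannot reliably rank five aeroallergens, and the text should not suggest that it can. If the best allergen doubles the attack rate and the others each raise it by 30%, some other allergen comes first in about 46-62% of studies (100 − 54 to 100 − 38) at a mean of 1 attack, and in about 33-56% (100 − 67 to 100 − 44) at a mean of 2.

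Every magnitude rests on assumed prevalence, attack frequency, effect size and overlap. The most favourable case examined, with frequent attacks, 20% prevalence per allergen and four inert competitors, reaches about 88%, so the right word is unreliable, not uninformative. The qualitative conclusion does not depend on very low prevalence: at 30 positives per allergen, power for a 20-point difference is still at most 48%, and the head-to-head comparison reaches only 22%. The absence of any planned comparison between allergens is a matter of record in Section 11 and needs no assumption.

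**What to change.** In Sections 6 and 7.1, replace the sentence with:

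> *For each aeroallergen, the number and proportion sensitised, the co-sensitisation pattern and the association with attacks will be reported with 95% CIs as exploratory, hypothesis-generating results; the study is not designed to identify the most useful allergen, and no allergen will be selected or dropped on p-values or rank.*

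Keep sensitisation to any aeroallergen (wheal ≥ 3 mm) as the atopy predictor, in line with the aim in Section 5, and keep the summed wheals of Section 4.1 as the exploratory graded measure. Retaining the per-allergen estimates matters: prevalence, overlap and attack rates by allergen, with intervals, are the inputs that a later power calculation needs and that the documents now lack.

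The cost is one sentence in two places. The small downside is that a stated claim is softened. No extra data collection is needed.

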7.2. INCLUSION AND EXCLUSION CRITERIA

7.2.1. CHILDREN

INCLUSION CRITERIA	EXCLUSION CRITERIA

1. Patients aged one to five years old presenting to primary care or to the emergency department or to secondary care (e.g., outpatients) or identified from primary care records and have been diagnosed with wheezing by their GP or paediatrician who has decided to prescribe any bronchodilator, ICS or montelukast on clinical grounds
	
1. Inability to understand and cooperate with study procedures
 
2. Significant co-morbidity (respiratory or otherwise), for example cystic fibrosis (excluding atopic disorders such as eczema, allergic rhinitis and food allergy)
 
3. Withholding or withdrawal of informed consent

2. Parents/Carers able to understand and familiarize themselves with the study and are willing to provide informed consent
	
4. Severe procedural anxiety (needle phobia)
 
5. Child is already enrolled in another study involving investigational medicinal product (CTIMP)
 
6. History of near-fatal asthma that resulted in intubation / assisted ventilation.

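### The three-month retest cannot isolate reproducibility of blood eosinophils and FeNO, because steroid treatment may change between the two tests

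*Combined protocol and SAP*

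**What the plan says.** Section 6 (repeated in 7.1, with the schedule in Appendix 2) tells parents that "a second optional testing will take place 3 months after the first one, in their second study visit". Its purpose follows: "This will allow assessing the reproducibility of the obtained biomarker results, thus additionally assess their stability".

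Other statements bear on what a change between the two tests can mean:

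- **Treatment is not controlled.** Section 6: "All treatment and routine monitoring decisions will be at the discretion of their treating general practitioner (GP) or paediatrician".
- **Children enter around a prescribing decision.** Section 7.2.1 requires a clinician "who has decided to prescribe any bronchodilator, ICS or montelukast on clinical grounds". ICS may therefore begin before or after the first test.
- **Treatment changes are expected.** Section 6 foresees ICS being stopped, and adds: "If an additional medication is prescribed, or the child is referred to secondary care, this will be considered as treatment failure". These events are used to label treatment outcome and are not linked to the retest.
- **ICS is expected to act on what two of the markers measure.** Section 4.1 describes eosinophil airway inflammation and its Type 2 cytokines with the words "which are responsive to inhaled corticosteroids (ICS"). For older children and adults it says that "titrating ICS dose using FeNO has been shown to reduce asthma attacks and improve outcomes".
- **The only steroid rule for test timing** is a two-week delay for oral corticosteroids.
- **FeNO has a same-visit repeat.** Exhaled breath "will be collected in a suitable bag in duplicate for offline measurement of FeNO". No analysis of the pair is described.

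Section 11 lists chi-squared, Fisher, t and Mann-Whitney tests. It has no agreement statistic and no split by treatment change.

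**The concern.** To learn how well a test reproduces, one repeats it while the child's underlying state is as near unchanged as possible. Here the repeat comes three months later, in children whose ICS may have been started, stopped or altered. A difference between the two results can come from measurement error, from natural or seasonal variation, or from treatment. The two results alone cannot say which.

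The study is a preliminary to a randomised trial of whether these markers predict response to ICS (section 5). A marker that falls on ICS may be behaving as section 4.1 would lead one to expect. If that fall is counted as poor reproducibility, the pilot gives its successor a misleading picture of the marker. Adding a kappa or an ICC would not cure this while children with changed and unchanged treatment are pooled.

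**Working it through.** **The plan's own figure.** There is none to reproduce. The documents give no reliability target, within-child SD, expected number of retests, share of children changing ICS, or effect of ICS on a marker. What follows is an illustration on assumed inputs.

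**Assumptions.** The marker is standardised to SD 1 at test 1. Same-condition reliability ρ = 0.75. The cut-off is the 70th percentile (30% positive). A share p of children start ICS between tests, unrelated to their marker level, and their value falls by d SD. Central case: p = 40%, d = 0.5. Range: p = 20–60%, d = 0.3–0.7.

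**Absolute-agreement ICC (concordance).** The covariance between tests stays at ρ. The variance at test 2 becomes 1 + p(1−p)d², and the squared mean difference is p²d². Hence

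ICC = 2ρ / (1 + 1 + p(1−p)d² + p²d²) = 2ρ / (2 + p·d²).

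- No change: 1.5/2 = 0.75
- p = 20%, d = 0.3: 1.5/2.018 = 0.74
- p = 40%, d = 0.5: 1.5/2.100 = 0.71
- p = 60%, d = 0.7: 1.5/2.294 = 0.65

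Only d² enters, so a rise after stopping ICS lowers agreement just as a fall after starting does.

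**Kappa and positives that turn negative.** From the bivariate normal with ρ = 0.75, the probability of being positive at both tests is 0.2004 for a child with unchanged treatment and 0.1229 for a child whose marker falls by 0.5 SD.

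*No change.*
- Positives turning negative: 1 − 0.2004/0.30 = 33.2%.
- Observed agreement: 0.2004 + 0.6004 = 0.8008. Chance agreement: 0.58.
- Kappa = 0.2208/0.42 = 0.53.

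*p = 40%, d = 0.5.*
- Positive at both: 0.6 × 0.2004 + 0.4 × 0.1229 = 0.1694.
- Positives turning negative: 1 − 0.1694/0.30 = 43.5%.
- Positive at test 2: 0.6 × 0.30 + 0.4 × 0.1528 = 0.2411.
- Observed agreement: 0.1694 + (1 − 0.30 − 0.2411 + 0.1694) = 0.7977.
- Chance agreement: 0.30 × 0.2411 + 0.70 × 0.7589 = 0.6035.
- Kappa = 0.1942/0.3965 = 0.49.

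| Share starting ICS, fall | Positives turning negative | Kappa | ICC |
|---|---|---|---|
| none | 33.2% | 0.53 | 0.75 |
| 10%, 0.3 SD | 34.8% | 0.52 | 0.75 |
| 20%, 0.3 SD | 36.3% | 0.52 | 0.74 |
| 40%, 0.5 SD | 43.5% | 0.49 | 0.71 |
| 60%, 0.7 SD | 54.5% | 0.43 | 0.65 |

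**Sensitivity.** With ρ = 0.80, p = 30% and a 1 SD fall, concordance is 1.6/2.3 = 0.70 instead of 0.80, and kappa is 0.50 instead of 0.58.

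**After the fix.** In children with unchanged treatment p = 0, so within this model the formula returns ρ itself.

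**Precision.** By Fisher's z with standard error 1/√(n − 1.5), an approximate 95% interval around 0.75 is 0.65–0.82 if all 100 children retest and 0.60–0.85 if 50 do.

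**The case against.** Five points can be made for the plan.

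1. **No misreading is written down.** A reader might infer that a falling marker will be classed as unreliable, or rejected. The documents do not support that: section 11 has no agreement analysis and no threshold for dropping a marker. The supportable statement is that a fall could be misread if the retest is used for its stated purpose.

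2. **The sentence also names stability**, which the retest can address under usual care. This stands. The unsupported part is the claim about reproducibility.

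3. **Not all three markers are affected alike.** A reader might extend the argument to skin prick tests. The documents nowhere say that those results fall with ICS. The argument is limited to eosinophils and FeNO, and for FeNO the titration evidence in section 4.1 comes from older children and adults. For skin tests only a procedural point remains: the site may be back, leg or arm, and nothing requires the same site twice.

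4. **The distortion is modest next to sampling error.** In the main table every ICC lies within the 95% interval around 0.75, even with 100 retests. This limits what one pilot could detect. It does not remove the bias, which does not shrink with more children.

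5. **The retest is optional and is named in neither the objectives (section 5) nor the outcomes (section 6.1).** This lowers the stakes, although the claim is made in two sections.

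**Conclusion.** The concern holds for blood eosinophils and FeNO. Used as sections 6 and 7.1 describe, the three-month retest measures stability under usual care and cannot isolate reproducibility. The only clean repeat in the design, the duplicate FeNO bags, has no stated analysis.

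The size is unknown from the documents. In the central illustration about 10 percentage points of positives turning negative (43.5% − 33.2%) would be treatment effect, with kappa 0.04 and ICC 0.04 lower. Over the range examined the figures are 36–54.5%, 0.52–0.43 and 0.74–0.65. The gap of about 21 points at the far end needs 60% of children to start ICS with a 0.7 SD fall, and nothing in the documents makes that the expected case. If few children change ICS, or were already on it at the first test and stay on it, the effect is small.

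A correction of wording and reporting is worth making before analysis. The point is not a reason to doubt the markers or to abandon the retest.

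**What to change.** - **Wording (sections 6 and 7.1).** Describe the retest as stability over three months under usual care. The same sections say the tests are done once, which should be reconciled with the optional second test.
- **Analysis (section 11).** For eosinophils and FeNO, name the agreement statistics: ICC or limits of agreement, and kappa at the cut-offs. Report them separately for children with and without an ICS change or an oral steroid course between tests.
- **FeNO repeatability.** Estimate the within-visit SD from the duplicate bags.
- **Data (Appendix 4).** Question 4 merges inhaled and oral corticosteroids with a single entry for dose, frequency and duration, so the split cannot be made cleanly from it. Divide it in two, or record ICS status at each test.
- **Secondary.** Record the skin-test body site and use the same site at retest.

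**Cost.** One more questionnaire item or test-day entry and a short addition to section 11, with no extra visit or sample. The unchanged-treatment subset will be smaller and probably weighted towards children whose wheeze stayed stable, so its agreement may not represent the whole cohort. Seasonal change remains in both groups.
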